The CTA will collect vital signs from each participant during the in-person visit and fill out digital forms (CTA Intake Form). The CTA will also provide the participants with study materials and randomly assigned and double-blinded interventions or placebo.

Subjects will be randomized with respect to which treatment or placebo they receive, and whether they get the placebo or treatment spray or lozenge. The spray will be applied every hour during waking hours and the tablet will be taken every four hours during waking hours. Subjects will be asked not to eat or drink anything for a few minutes after administration.

Subjects will be asked at four-hour intervals during waking hours to rate their sore throat pain on a validated, paper-based sore throat pain scale, Sore Throat Pain Intensity Scale (STPIS) consisting of a 100mm line along which participants mark their pain intensity (Schactel et al., 2014 and references therein).

The study will end when participants complete their second day of treatment and surveys.

The study will be conducted in a double-blind format, neither the participant nor the CTA, CTM, or PI will know whether the participants are getting treatment or placebo. Participants will be coded and randomized by a third party as the treatments are bottled.

The study will only be unblinded at the end of the study after the data analysis has been completed and by the Adverse Events Specialist (AES) in the case of adverse events.

STUDY POPULATION

Healthy adults, half male, half female, aged 18-65 with no history within the past 30 days of serious allergy, asthma, nasal or otologic disease, and no symptoms of upper respiratory infection (URI). After age 65 many of the exclusion criteria listed below become more common. We feel it is important to enroll an equal number of males and females to control for gender bias in the data.

This will be controlled for in the recruitment process and adjusted if needed by controlling social media targeting criteria. Initially the target population will be: age 18-65, living in the Washington DC/northern Virginia area, retired, government employee, teacher, non-active duty military personnel, or college student.

INCLUSION AND EXCLUSION CRITERIA

Inclusion

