Based on a similar prior study of an NSAID containing lozenge for sore throat (Schachtel et al., 2014) a 59% decrease in time weighted summed difference for STPIS over 24 hours was seen with a p-value less than 0.01 with a sample size of 198 participants.

PROCEDURES AND DATA COLLECTION

Paper-based Patient Forms will be mailed to a PO Box monitored by the PI and the DA, located in Rockville MD. Survey assessments will be measured in mm from the beginning of the line and recorded on an Excel spreadsheet according to kit number (Participants will not be identified by name).

FOLLOW-UP

Participants will be able to contact the PI, CTA, and CTM at any point during the trial. They will be encouraged to contact the trial staff should they suspect any adverse events including fever above 101 at which point a determination will be made by the PI or AES if they should continue. Participants will not be followed after the study ends. Other serious adverse events that the PI will discuss with participants include nausea or vomiting, difficulty breathing, and/or breaking out in a rash or hives.

If anyone else should require information gathered from this study, they will only receive the participant's code number, age, sex, ethnicity, but no other identifying information.

DATA AND SAFETY MONITORING

Participants will self monitor at home and fill out the survey questionnaire at the required time points. Participants will be encouraged to call 911 in case of emergencies such as anaphalactic shock and high fever. The PI and CTM will be available for questions and non-urgent matters.

The AES will be available to address serious adverse events and will unblind the study in cases such as high fever where the participant may be harmed by being in the placebo group, or for any other medically necessary reason.

DISCONTINUATION OF RESEARCH PARTICIPANTS/WITHDRAWAL

Participants will be able to voluntarily discontinue at any point in the study by calling the CTM.

RECORD RETENTION

In the event of any publication or presentation resulting from the research, no personally identifiable information will be shared.

REPORTABLE EVENTS

As required by Policy IRB-01, all reportable events will be reported to the IRB within the specified deadlines. Additional information is provided in the IRB Guidance on “Reportable Events.” Events are defined in the IRB Guidance on “Acronyms and Definitions.” For additional information see: <http://research.downstate.edu/irb/irb-policies.html>

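### The plan describes no active collection of adverse events and rules out observation after the last dose, so harms will tend to be under-counted by an amount that cannot be calculated

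*Combined protocol and SAP*

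**What the plan says.** All references are to the combined protocol and SAP.

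- **End of observation.** Overview of the Study Design: "The study will end when participants complete their second day of treatment and surveys." Follow-Up: "Participants will not be followed after the study ends."
- **Route by which events reach staff.** Follow-Up: "Participants will be able to contact the PI, CTA, and CTM at any point during the trial." And: "They will be encouraged to contact the trial staff should they suspect any adverse events including fever above 101." The same section lists further events that the investigator will talk through with participants: nausea or vomiting, breathing difficulty, and rash or hives. It classes them as serious.
- **Monitoring at home.** Data and Safety Monitoring: "Participants will self monitor at home and fill out the survey questionnaire at the required time points."
- **What the questionnaire is said to contain.** Overview: "Subjects will be asked at four-hour intervals during waking hours to rate their sore throat pain on a validated, paper-based sore throat pain scale." The Modified Jackson Score for cold symptoms is named as a secondary efficacy endpoint, and its items are not listed.
- **Handling of the forms.** Procedures and Data Collection: "Paper-based Patient Forms will be mailed to a PO Box monitored by the PI and the DA." Marks on the line are then measured and entered by kit number. No adverse-event field is mentioned.
- **Withdrawal.** Discontinuation section: "Participants will be able to voluntarily discontinue at any point in the study by calling the CTM." The text does not say what is asked or recorded at that call.
- **Analysis.** The Analysis Plan names efficacy endpoints only and describes no adverse-event table.

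**The concern.** The plan expects harms. It names several, appoints an Adverse Events Specialist (AES), and lets the investigator or AES judge whether a participant should continue. Each of those steps depends on someone first learning of the event. Yet the described route relies mainly on the participant recognising an event and making contact, and planned observation stops when dosing stops.

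Two things are at stake. The first is participant safety: people dose themselves at home, hourly with the spray and four-hourly with the tablet while awake, and no planned contact would pick up a reaction that starts after day 2. The second is interpretation: a low recorded count could reflect few harms or few reports, and the data would not tell the two apart.

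**Working it through.** **1. The plan's own figure.** There is none to reproduce. The documents give no adverse-event rate, no reporting rate and no safety sample size.

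**2. The described routes, side by side.**

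| Route | Who starts it | Described as asking about adverse events? | Planned after the last dose? |
|---|---|---|---|
| Contact with staff (Follow-Up) | Participant | No, it depends on suspicion | No, offered during the trial |
| Four-hourly paper form (Overview; Data and Safety Monitoring) | Participant | No item described | No |
| Vital signs (Overview) | Staff | Not described; taken at the in-person visit | No |
| Withdrawal call (Discontinuation) | Participant | No recording step described | No |
| IRB reporting (Reportable Events) | Staff | Covers events already known | Not a detection route |

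No row is a scheduled safety question put by staff.

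**3. Planned time at risk after dosing.** The window is the end of follow-up minus the last dose. Both fall at the end of day 2, and later follow-up is excluded, so the planned window is zero. This comes from an explicit rule, not from silence.

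**4. Illustration of scale.** Let p be the true share of participants with an event and c the share of those events that is recorded, both assumed. Take n = 100 per arm (400 enrolled ÷ 4 conditions).

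- Expected recorded events = n × p × c
- Chance of recording at least one = 1 − (1 − p × c)^n

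Each cell gives expected events, then the chance of at least one:

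| p | c = 1 | c = 0.75 | c = 0.5 | c = 0.25 |
|---|---|---|---|---|
| 1% | 1.0; 0.63 | 0.75; 0.53 | 0.5; 0.39 | 0.25; 0.22 |
| 2% | 2.0; 0.87 | 1.5; 0.78 | 1.0; 0.63 | 0.5; 0.39 |
| 5% | 5.0; 0.99 | 3.75; 0.98 | 2.5; 0.92 | 1.25; 0.72 |
| 10% | 10.0; 1.00 | 7.5; 1.00 | 5.0; 0.99 | 2.5; 0.92 |

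Example: p = 2%, c = 0.5 gives 1 − (1 − 0.01)^100 = 0.63.

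**5. Effect on a comparison of arms.** Suppose true rates of 2% and 10%, 100 per arm, two-sided 5%, and the same c in both arms. With recorded rates r0 = 0.02c and r1 = 0.10c, and r̄ their mean:

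power = Φ{[(r1 − r0)√n − 1.96√(2r̄(1 − r̄))] ÷ √(r0(1 − r0) + r1(1 − r1))}

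At c = 1 this is Φ{(0.800 − 0.658) ÷ 0.331} = 0.67. It falls to 0.38 at c = 0.5 and 0.21 at c = 0.25.

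For events starting after day 2, planned capture is zero; only an unprompted call would reveal them.

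**The case against.** The best defence is that much of this is silence rather than a stated defect. The questionnaire appears under the safety-monitoring heading and is not reproduced in full, so an adverse-event item may exist. Participants are told which events to watch for and have staff contacts. The Clinical Trial Manager (CTM) may well ask why someone is leaving. Spontaneous reporting under a double blind need not differ by arm. All of that stands, and it rules out several stronger readings a reader might infer:

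- **That events are captured only by a call, or that nobody would hear of a late reaction.** The text shows that no other route is described and no later contact is planned. An unprompted call remains possible.
- **That no reason or event is taken at withdrawal.** The text does not say either way.
- **That half of those enrolled would leave with no event check.** The 50% in the Analysis Plan combines drop-out with exclusion. Some exclusions, such as a positive infection or pregnancy test at the home visit, arise around intake, so those people may never take a dose. The split is not given.
- **That every active arm carries aspirin risk.** The Introduction describes treatments with and without aspirin, and the text does not give the composition of each arm.
- **That no safety comparison could be made.** If under-reporting is similar in all arms, comparison is weakened, as step 5 shows, but not excluded.

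What survives is enough. The exclusion of follow-up is explicit. Even if the form did hold an event item, a posted form would not be a prompt signal and would not cover the time after day 2. Counselling participants on what to watch for is not a recorded, scheduled question.

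**Conclusion.** The point holds as a shortfall in ascertainment. As written, the plan gives zero planned observation after the last dose and describes no solicited event question, no staff-initiated safety contact and no event-recording step at withdrawal. The recorded harm count will tend to be too low, and late-onset events will tend to be missed.

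Only the direction follows from the documents. The tables rest on assumed event rates of 1% to 10% and assumed capture of 25% to 100%, equal across arms and unrelated to drop-out. They show sensitivity and are not estimates. The point does not touch the primary efficacy comparison. It should be acted on because the remedy is specific, inexpensive and uses staff already in place.

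**What to change.** 1. **Form.** Add a tick-box line to the existing four-hourly form for the events that Follow-Up names, plus an other category, with onset time. Because the forms are posted, this improves counting rather than prompt detection.
2. **Call after the last dose.** Replace the sentence that excludes follow-up with one scripted call by the blinded CTM to every participant who took at least one dose, including those who withdrew. Pass positive answers to the investigator or the AES. The sponsor should fix the timing in advance, since it sets the length of the observed window; events starting after the call would still go unsolicited.
3. **Withdrawal.** Use the same script when a participant calls to withdraw, and record the reason.
4. **Reporting.** Add a planned table of solicited events by arm, with dosed participants as the denominator and the number reached by the call shown alongside.

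**Cost.** A protocol amendment, one short call per dosed participant (at most about 400), repeat attempts for non-responders, and added data entry. The recorded event count will probably be higher; that reflects better capture and should be expected when the results are read. No dose, eligibility rule or treatment decision changes.

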Healthy adults between the ages of 18-65 that do not meet any of the exclusion criteria listed below, and who rate their sore throat at least a 3 on a 10 point scale, and who have had a sore throat for less than 48 hours by the time they complete the CTM assessment.

Exclusion

Sore throat for more than 2 full days at the time of CTM assessment

Fever or development of fever during the course of the trial

Positive COVID-19 test or influenza test at CTA visit

Likelihood of strep throat (to be determined by PI to the best of their ability)

Less than 2 doses of the COVID vaccine

Any allergies to eggs, milk, or aspirin

Females who are pregnant or test positive for pregnancy at the CTA visit

Any chronic disease such as asthma, hypertension, post-nasal drip, gastroesophageal reflux disease (GERD), cardiopulmonary obstructive disorder (COPD), diabetes, cancer, HIV

Any history of allergy in the last 14 days for which they took medication

Anyone with fever above 101 or who has taken medication other than birth control in the last 30 days

Anyone taking an ACE inhibitor

Participation in another clinical trial within the last 6 months or during this trial

Anyone who smokes

STATISTICAL CONSIDERATIONS

ANALYSIS PLAN

The design of this study will be a between patient, non-crossover, randomized controlled trial. The primary endpoint of this study is a time-weighted summed difference in pain intensity on the sore throat pain intensity scale over 36 hours after the first dose of medication (STPIS 1st entry Day 1 compared to STPIS 4th entry Day 2). For the study to have 80% power and 20% effect size, we believe we will need at least 100 participants per condition. Our hypothesis is that the patented Mucosal Immune Complex (MIC) will decrease STPIS score by 25-50%. Our assumptions and our hypothesis are based on a previous study utilizing this endpoint with an average baseline STPIS score of 79.1 (+/- 8.2) (Schachtel et al., 2014). Assuming a 50% drop-out or exclusion rate, we aim to enroll a total of 400 participants across all four conditions.

Efficacy will be determined by t-test comparing time-weighted summed differences in STPIS scores for placebo and MIC treatment groups. Secondary endpoints will include changes in STPIS at different time points and changes in Modified Jackson Score over the course of the study.

SAMPLE SIZE JUSTIFICATION

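### The plan does not separate stopping treatment from leaving the study, and makes no provision to collect pain scores after stopping

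*Combined protocol and SAP*

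**What the plan says.** The section headed DISCONTINUATION OF RESEARCH PARTICIPANTS/WITHDRAWAL is one sentence: "Participants will be able to voluntarily discontinue at any point in the study by calling the CTM". It does not say what is discontinued: the spray, the tablet, the pain ratings or all of them.

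Two further routes out appear elsewhere.

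- Under FOLLOW-UP, participants are encouraged to contact staff about suspected adverse events, including fever above 101, "at which point a determination will be made by the PI or AES if they should continue". What they would continue is not defined.
- Under INCLUSION AND EXCLUSION CRITERIA, the exclusions include "Fever or development of fever during the course of the trial". The second half of that line can only apply to someone already in the trial.

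On data collection, OVERVIEW OF THE STUDY DESIGN has pain rated on paper every four waking hours and states: "The study will end when participants complete their second day of treatment and surveys". DATA AND SAFETY MONITORING adds: "Participants will self monitor at home and fill out the survey questionnaire at the required time points". PROCEDURES AND DATA COLLECTION says: "Paper-based Patient Forms will be mailed to a PO Box monitored by the PI and the DA". FOLLOW-UP says: "Participants will not be followed after the study ends". None of these covers the time between stopping the product and the end of Day 2.

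ANALYSIS PLAN defines the primary endpoint as a time-weighted summed difference in STPIS over 36 hours, up to the fourth entry of Day 2, compared by t-test. It names no analysis set and no rule for missing scores. The same section plans for heavy loss: "Assuming a 50% drop-out or exclusion rate, we aim to enroll a total of 400 participants across all four conditions".

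**The concern.** Randomisation protects the comparison only as far as outcomes are obtained from everyone randomised. People may stop an hourly spray and a four-hourly tablet because the pain has gone, because it has not gone, or because the product disagrees with them. Each reason is plausibly related to pain, and each may be more common in one arm than another. If scoring stops when dosing stops, the endpoint is missing or cut short for these participants, and a t-test on the scores that happen to be available may compare selected groups.

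The gap cannot be closed afterwards. An analysis can make assumptions about scores that were never recorded, but it cannot recover them. The protocol is therefore the place to deal with it.

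**Working it through.** **Step 1. The routes out, side by side.**

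| Route | Section | Does treatment end? | Does scoring end? | Is the part-filled form requested? |
|---|---|---|---|---|
| Participant calls the CTM | Withdrawal | not said | not said | not said |
| PI or AES decides | FOLLOW-UP | not said | not said | not said |
| Fever during the trial | Exclusion criteria | not said | not said | not said |

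The second and third routes overlap. A participant who becomes febrile meets an exclusion criterion, yet with fever above 101 also falls under a case-by-case decision on continuing. The passages must be reconciled.

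**Step 2. The loss that the plan allows for.** The plan gives no figure for bias, so there is none to reproduce. Its relevant figure is the 50% allowance: 400 × (1 − 0.50) = 200 contributing, or 200 / 4 = 50 per condition if allocation is equal (an assumption, as the ratio is not stated). The plan says that it needs at least 100 per condition. That mismatch is a separate sample-size matter. It is used here only to show that loss is a planning assumption and not a remote risk.

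**Step 3. Bias on an average-score scale.** In one arm, let f be the fraction lost, R the mean of those retained and L the mean of those lost. The mean of all randomised is (1 − f)R + fL, so the retained mean differs from it by f(R − L). With the same f in both arms:

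bias = f × (gap in one arm − gap in the other)

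The gaps are assumptions; the documents give none.

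- Gap 10 mm in one arm, 0 in the other, f = 0.10: 0.10 × 10 = 1 mm.
- Same gaps, f = 0.50: 0.50 × 10 = 5 mm.
- Gap 5 or 15 mm in one arm only, f = 0.50: 0.50 × 5 = 2.5 mm; 0.50 × 15 = 7.5 mm.
- Same gap in both arms: 0 mm at any f.

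The f = 0.50 results are upper figures, because the plan's 50% covers exclusions as well as drop-out.

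**Step 4. A second illustration, with unequal loss.** Assume no true effect, 100 randomised per arm, a normal outcome with SD 1 and a two-sided 5% test. In each arm the fraction p that leaves is the lowest on a latent variable correlated ρ with a good outcome. The mean of those retained then shifts by ρ × φ(z_p) / (1 − p), where φ is the normal density and z_p the p-quantile. The bias is the difference in shifts between arms. For p = 0.60 and 0.40, φ is 0.386 in both, so the bias is ρ × (0.386/0.40 − 0.386/0.60) = ρ × 0.322.

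| Loss in the two arms | Bias, ρ = 0.3 to 0.7 | False-positive rate |
|---|---|---|
| 50% / 50% | 0 SD | 5% |
| 55% / 45% | 0.05 to 0.11 SD | 5.7% to 8.6% |
| 60% / 40% | 0.10 to 0.23 SD | 7.6% to 19.7% |

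Under this mechanism the arm that loses more of its poor responders looks better than it is, so the bias could favour either side. Both illustrations show that bias needs a between-arm difference in how loss relates to outcome. Heavy loss alone is not enough.

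**The case against.** The strongest reply is that silence is not a rule. A reader might infer that the withdrawal sentence is the only one, that it makes stopping treatment and leaving the study a single act, that later scores are lost, and that the primary comparison rests on those who kept dosing. The documents support none of these.

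- There are at least three routes out, as shown above.
- No text equates stopping treatment with leaving. The sentence on study end, which names treatment and surveys together, describes people who complete.
- The four-hourly rating request is not made conditional on dosing. The forms are filled in at home and mailed, so someone who stops the spray without calling is still asked to score and could still be analysed.
- No analysis set of any kind is stated, so neither is one restricted to those who kept dosing.

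All of this stands, and it limits the finding to what is undefined and what may follow.

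Consent pages were also removed from the text available, and the participant materials are not reproduced. Either may ask people to return forms. The finding therefore concerns the protocol and SAP text only.

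On size, a reader might set 5 mm against 20% of the cited baseline, 0.20 × 79.1 = 15.8 mm, and conclude that a third of the effect is at risk (5 / 15.8 = 32%). That does not stand. The plan does not define its 20% effect size. The endpoint is a 36-hour sum, not a single score. The stated hypothesis is a 25-50% decrease, or 19.8 to 39.6 mm, against which 5 mm is 25% to 13%. Some of the 50% may also be exclusions found at the home visit, such as a positive COVID-19, influenza or pregnancy test, possibly before any dose.

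What remains is that nothing in the text tells staff or participants what to do about scoring once someone stops, or tells the analyst what to do with that person's data.

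**Conclusion.** The point holds as an undefined procedure with a plausible consequence. The plan does not distinguish stopping study treatment from leaving the study on any route out. It does not provide for continued STPIS collection or retrieval of partial forms, and it does not say how those who stop enter the primary t-test. Because the endpoint needs serial scores to the fourth entry of Day 2 and the plan assumes 50% drop-out or exclusion, scores may be lost for reasons related to pain and arm, and the comparison may rest on selected participants.

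The size cannot be derived from the documents. The range of 1 mm (10% loss) to 5 mm (50% loss) rests on an assumed 10 mm gap in one arm only, equal loss in both arms and an average-score scale. The SD figures rest on an assumed dropout mechanism, significance level and 100 randomised per arm. If loss relates to outcome in the same way in every arm, the bias is nil and only precision suffers. Confidence is medium. The change is worth making because it costs little and cannot be made after the data are in.

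**What to change.** 1. Define stopping study treatment separately from withdrawing consent to data collection, and apply the definitions to every route: the participant's call, the PI or AES decision, and fever during the trial. Reconcile the fever exclusion with the decision on continuing; no clinical rule is proposed here.
2. State in the protocol and on the participant instructions that anyone who stops the spray or tablet for any reason, relief included, is asked to keep completing STPIS to the fourth entry of Day 2 and to mail the form even if partly filled, unless consent to data collection is withdrawn. A CTM call script alone would miss those who stop without calling.
3. Record the reason and time of stopping against the kit number.
4. Analyse all randomised participants as assigned, using every score collected. Pre-specify a method for scores still missing, with a sensitivity analysis.

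The cost is a few protocol sentences, a line on the instructions, a short call script and a paragraph in the analysis plan. The forms are already in the home and the study lasts two days. The downside is a few more entries for people who have stopped dosing, and an effect estimate that includes time off treatment and so may be slightly smaller.
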